Patients presenting with, or developing during the study period, severe actue renal failure requiring renal support, will receive continuous renal replacement therapy (CRRT) as per standard local practices. This would apply to subjects in both SOC and DIALIVE arms. For those in the DIALIVE arm, the same vascular catheter which is used for DIALIVE treatment may be used for CRRT following the completion of the DIALIVE treatment session. It is however envisaged

that increased intensity of dialysis component in the DIALIVE system (from 1lit/hr to 1.5lit/hr) and allowance for fluid removal in the new protocol may delay or remove altogether the need for CRRTin these situations. The decision for additional CRRT would depend on clinical situation and will be taken by the site PI.

DIALIVE arm consists of standard of care (defined above), plus DIALIVE treatment.

A DIALIVE treatment session denotes treatment for the day, whereas A DIALIVE treatment cycle refers to the total number of treatment days.

A DIALIVE treatment **session** = A minimum, cumulative duration of 8 to 10 hrs (± 30 min) of the DIALIVE treatment, thus allowing for breaks which may be planned (for example patients needing to go for imaging) or unplanned (device clotting, issues with vascular access or other any other unplanned reasons). A break within a treatment session (consisting of a cumulative time longer than 4hrs), or a cumulative duration of less than 8 hrs of dialysis during one day constitutes a session failure for that day. A session failure will require to restart the dialysis session within 24 hrs after the end of the previous session and will reset the start of the dialysis cycle.

A DIALIVE treatment **cycle**= Consists of 3 consecutive days of 8-10 hrs of DIALIVE treatment sessions on each day within the 10 day window period. A break of more than 24hrs between each treatment session will require a new baseline (i.e. a new treatment cycle commenced). A second failed treatment session within the 10 day window period would result in patient exlusion. The patient must have completed one successful treatment cycle within the 10 day window period to be considered evaluable.

Day of randomization constitutes study Day 0.

The first treatment session (DIALIVE arm only) must commence before the end of study Day 1. As such, dialysis might also start on the day of randomization which might created confusion as 'the first day of dialysis' then concurs with DAY 0 of the study schedule.

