- Replacement fluid (pre-dilution solution) to start at a rate of 1000 ml/hr and increased gradually to up to 3500 mls/hr (50mls/kg/hr for a 75 kg person) subject to haemodynamic stability. Concomitant dialysis component to run at 1500 mls/hr (25 ml/kg/hr for a 75 kg person).
- Albumin is exchanged simultaneously with DIALIVE treatment. Infusion of fresh albumin will be through the HepAlbin filter at a rate of 5 g/hr (to replace albumin removed by the device). This equates to an infusion of 20% human albumin solution at a rate of 25mls/hr.
- Mean arterial pressure is to be continuously monitored, and MAP is maintained at 90% or higher of pretreatment MAP or above 65 mmHg, whichever is higher.
- 2-hourly blood gas analysis (including lactate), and 4 hourly other bloods (FBC, U/E, LFT, coagulation) at 0, 4 and 8-12 hrs (end of treatment) should be performed.
- A senior staff member will closely supervise the dialysis procedure during the first few hours of treatment, with a clear internatl escalation plan available, and discuss with study CI where necessary
- Effluent of dialysis fluid from the effluent line AND waste collection bag to be collected a 0-1, 4, 8-10 hrs (end of treatment) as part of biobank samples.

- Following completion of treatment session:

- Blood within the circuit is to be returned back to the patient, unless the filter is clotted.
- Repeat Haemolysis screen (at end of session of D1 only)
- EAA-analysis (end of days 1, 2 and 3)
- Ensure treatment data is stored in the device and retrieved at a later date
- Blood to be collected as part of biobank samples. (end of days 1, 2, 3)

2.3 Details concerning the manufacturer and traceability of the investigational device.

Membrane ⁹ :	septeX™ Haemofilter	oXiris® Haemofilter
Manufacturer:	Baxter, USA	Baxter, USA
Indications:	Continuous renal replacement therapy for subjects with acute renal failure	For subjects who have acute renal failure, fluid overload or both.
Intended use:	Continuous veno-venous haemodialysis (CVVHD) in conditions where the removal of plasma components with molecular weights up to a value of 45 kDa, such as substances that mediate inflammation, is indicated	Veno-venous therapies: slow continuous ultrafiltration (SCUF); continuous veno-venous haemofiltration (CVVH); continuous veno-venous haemodialysis (CVVHD); continuous veno-venous haemodiafiltration (CVVHDF)

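### Two slips in Section 2.2: the per-kg doses in brackets do not match the ml/h rates at 75 kg, and the ± 30 min session tolerance contradicts the rule that under 8 hours is a failed session

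*Protocol*

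**What the plan says.** **Flow rates.** The ready reference in Protocol Section 2.2 gives each rate in ml/h, with a per-kg equivalent in brackets:
- Replacement fluid is raised stepwise "up to 3500 mls/hr (50mls/kg/hr for a 75 kg person"), subject to haemodynamic stability.
- For dialysate the text is "Concomitant dialysis component to run at 1500 mls/hr (25 ml/kg/hr for a 75 kg person").
- The paragraph on renal replacement therapy in the same section confirms the dialysate rate independently: "increased intensity of dialysis component in the DIALIVE system (from 1lit/hr to 1.5lit/hr").

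**Session length.** Section 2.2 states the length three times:
- The session is "A minimum, cumulative duration of 8 to 10 hrs (± 30 min) of the DIALIVE treatment".
- The failure rule is that "a cumulative duration of less than 8 hrs of dialysis during one day constitutes a session failure for that day".
- The cycle is "3 consecutive days of 8-10 hrs of DIALIVE treatment sessions on each day within the 10 day window period", with no tolerance.

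**Consequences.** A failed session "will reset the start of the dialysis cycle". Beyond that, "A second failed treatment session within the 10 day window period would result in patient exlusion". One successful cycle inside the 10-day window is what makes a DIALIVE patient evaluable.

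**The concern.** The two slips differ in kind.

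The brackets are plain arithmetic. They stand in the reference that site staff use at the bedside, in a study that Section 5.5 rates as high risk. A site that worked from ml/kg/h would set a different rate from one that followed the ml/h figure. Nothing in the analysis depends on them.

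The session tolerance touches a decision rule. If one sentence accepts a session that another fails, two sites can classify the same session differently, and the trial is open label. The classification feeds:
- cycle reset and exclusion (2.2);
- replacement of patients who are not evaluable (5.1.7);
- the point at which a cohort of 6 evaluable patients is complete (5.2);
- the evaluable set used in the safety sensitivity analysis (6);
- the choice of the cycle used for end-point analysis (7.1.1), including the 20% and 40% reductions read at the end of the treatment cycle (5.1.3).

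Each cohort has only 3 DIALIVE places, so one disputed session can change a cohort's make-up.

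**Working it through.** **1. Flow rates (inputs from Section 2.2: 1500 and 3500 ml/h; 25 and 50 ml/kg/h; 75 kg).** The stated per-kg figures cannot be reproduced.

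| Component | Rate ÷ 75 kg | Stated | Stated ÷ correct | Stated × 75 kg | Weight that fits |
|---|---|---|---|---|---|
| Dialysis | 1500/75 = 20.0 ml/kg/h | 25 | 25/20 = 1.25 | 1875 ml/h | 1500/25 = 60 kg |
| Replacement fluid | 3500/75 = 46.7 ml/kg/h | 50 | 50/46.7 = 1.07 | 3750 ml/h | 3500/50 = 70 kg |

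The brackets fit 60 kg and 70 kg, so no single body weight makes both right. The excess is 25% for dialysis and 7% for replacement fluid. The second could be loose rounding of a maximum; the first could not. Because 1.5 l/h is repeated elsewhere in Section 2.2, the ml/h rates are the intended order and the brackets are the error.

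**2. Session length.**
- Lower limit with the tolerance: 8 − 0.5 = 7.5 h.
- Lower limit under the failure rule: 8 h.
- Lower limit in the cycle definition: 8 h.
- Band with two answers: 7.5 to under 8 h.
- Shortest successful cycle: 3 × 7.5 = 22.5 h with the tolerance, 3 × 8 = 24 h without it.

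Two of the three statements point to a strict 8 hours. The tolerance is the outlier.

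**3. What turns on it.** Take sessions of 8 h, 8 h and 7 h 45 min.
- With the tolerance, the cycle is complete at the third session. The patient is evaluable and the end-of-cycle reductions are read there.
- Under the failure rule, the third session fails and the cycle restarts. The patient needs three further sessions, so the end of cycle moves to the sixth. One more short session excludes the patient, who is then replaced.

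**4. Who can be affected.** Appendix 9 (used here only to date the rule) places the cycle of three 8–10 hour sessions in version 6.0. That version already includes the safety board's review of cohort 2 (Appendix 7). At most cohorts 3 to 5 were treated under it: 3 cohorts × 3 = 9 evaluable DIALIVE places. The share of sessions lasting 7.5 to under 8 h is not given, so the number of patients affected cannot be derived.

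**5. What is not affected.** The main analyses use the safety population (6), and the synopsis counts any duration of exposure as a treatment. Session classification does not enter.

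**The case against.** The best defence is that a careful reader can already settle the session rule. The duration is called a minimum, an explicit failure rule follows, and the cycle definition repeats the range without a tolerance. The ± 30 min would make sense as an allowance above 10 hours. Much of this stands, and it is why 8 hours is the natural choice. It does not remove the conflict: the text attaches the tolerance to the whole range and nowhere limits it to the upper end.

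The reach is also modest. All analyses are descriptive, the evaluable set serves one sensitivity analysis, and staff can usually extend a session that is running short. Recruitment was expected to run until December 2019, or to about May 2020 if the 39 months are counted from February 2017. An amendment after version 7.0 of October 2019 may therefore reach few patients. All of that stands.

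A reader might also infer more than the documents support:
- **That the end-of-treatment bloods at 8–12 h are wrong.** Section 2.2 times blood samples from connection, while session length is cumulative treatment time. Breaks fail a session only when they total more than 4 h, so a valid 8-hour session can end up to 8 + 4 = 12 h after connection. Narrowing the window could put the sample before the end of treatment. Version 7.0 shortened the effluent window and not this one, but that does not show an error.
- **That the 12-hour albumin example in Section 2.1 is wrong.** The instruction is 5 g per hour, and 5 × 12 = 60 g is correct.
- **That the exclusion list in Section 2.2 is defective because it omits the second failed session.** The trigger is stated in the same section.
- **That a number of wrongly excluded patients can be given.** Any such count rests on an assumed share of short sessions.

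**Conclusion.** Both errors stand in the current text. The dialysis bracket overstates the per-kg dose at 75 kg by 25%, and the replacement-fluid bracket overstates it by 7%, possibly through rounding. The documents do not show that any patient was dosed wrongly, since the ml/h rates are the order.

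The session rule gives two answers for any session of 7.5 to under 8 hours. This can change cycle reset, exclusion, evaluability, replacement, cohort completion, the evaluable sensitivity set and the end-point cycle, for at most the 9 evaluable DIALIVE places in cohorts 3 to 5. The effect could be nil if every session reached 8 hours. The main serious adverse event comparison is untouched. The finding is well supported and worth correcting, but limited in reach.

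**What to change.** 1. Keep 1500 ml/h and the maximum of 3500 ml/h. Change the brackets to 20 and about 47 ml/kg/h, or delete them.
2. Make 8 hours cumulative the single failure threshold by removing the lower tolerance, unless the sponsor documents that 7.5 hours was intended. If so, set the failure limit at under 7.5 hours and align the cycle definition.
3. Apply the change prospectively and do not reclassify patients already treated. Until approval, plan every session for at least 8 hours, which satisfies both readings.
4. Report how many sessions lasted 7.5 to under 8 hours and how each was classified.
5. Leave the 8–12 h blood sampling and the albumin example as they are.

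**Cost.** A few words in Section 2.2. A changed failure threshold needs ethical and regulatory approval before use (Section 8), so it is best joined to the next amendment. No new data collection is needed, because Section 2.2 already has treatment data stored in the device and retrieved later.

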2.4 Device materials that will be in contact with tissues or body fluids

Membrane	septeX™ Haemofilter	oXiris® Haemofilter
Housing	Polycarbonate	Polycarbonate
Potting compound	Polyurethane	Polyurethane
Tubing	Plasticized polyvinyl chloride	Plasticized PVC
Cartridge plate	Polyethylene terephthalate glycol-modified (PETG)	PETG

Fig 1. DIALIVE Liver Dialysis Device (LDD) as incorporated into the extracorporeal circuit. Filter set 1 + 2 + interconnecting tubing constitutes the DIALIVE unit, rest is standard dialysis equipment

Clinical Investigation Plan CIP YAQ-002 Version: 7.0 10 October 20	19
--	----

2.5 Summary of the necessary training and experience needed to use the investigational device.

The main end users of the LDD are expected to be the Hepatologists, Intensive care physicians, Renal physicians and the Liver transplant surgeons, all of whom have extensive experience in using dialysis and haemofiltration equipment. Training on the DIALIVE device set up will be provided to each site by Yaqrit (sponsor) who has experience in the DIALIVE delivery. The set up and Instructions For Use (IFU) are outlined in the Investigator's Brochure and a separate IFU and will be provided to each site.

2.6 Description of the specific medical or surgical procedures involved in the use of the investigational device.

Patients randomised to receive DIALIVE liver dialysis treatment will be treated in a high dependency setting (HDU), or Intensive Care Unit (ICU) to ensure provision of expertise in the use of the Liver Dialysis Device and provision of continuous monitoring whilst the patient is receiving DIALIVE liver dialysis treatment. Please see § 2.2. Definitions.

2.7 Current Standard of Care and Need for Improvement

Two-hundred and sixty epidemiological studies from 8 different European countries between 2008 and 2013 [1] estimated that liver cirrhosis affected 0.1% of the total EU population with an incidence of 14- 26 new cases per 100,000 inhabitants and about 170,000 deaths per year [1]. Although the overall mortality rate for liver cirrhosis slightly declined in Europe (as well as in USA) from 1980 to 2010 due to better management and control of liver diseases and alcohol consumption; it increased in Eastern European countries, the United Kingdom and Ireland [2]. The only available treatment for cirrhosis and liver failure patients is liver transplantation, and with the shortage of donors world-wide about 1 million patients die from liver failure each year.

The number of liver transplants performed each year is limited by organ availability and over the past 15 years, the number of transplants in Europe has plateaued at about 6000/year (European Liver Transplant registry; ELTR.org). A recent analysis of the Eurotransplant data of over 16,000 patients listed for liver transplantation in Europe, 27.8% died while waiting for a suitable organ for transplantation become available [3]. Consequently, there is a clear need to find regimes which can be used to maintain and improve the condition of such patients requiring transplant [4].

Liver transplantation is the only treatment for patients with liver failure and an alternative to this remains an unmet need. In Acute Liver Failure (ALF), the ideal LDD would replace the functions of the failing liver in order to permit spontaneous recovery as the liver's powerful regenerative potential obviates the need for transplantation. In patients with Acute on Chronic Liver Failure (ACLF), an LDD would ideally support hepatic function during a period of acute deterioration until spontaneous recovery from the episode of decompensation. It would allow time for drugs to address the precipitating event or the underlying the liver disease. In patients with decompensated cirrhosis, a LDD could support hepatic function until liver transplantation. In addition, LDDs may have potential to treat the multi-organ failure that accompanies liver failure including hepatic encephalopathy, renal failure and immune dysfunction.

Acute decompensation (AD) or cirrhosis complicated with organ failure (ACLF) has a mortality rate of 30-40% and death is mostly related to multiple organ dysfunction [5]. The condition is widespread, affecting about 30% of all hospitalised cirrhotic patients and has a 28-day mortality of about 30% [6, 7]. Furthermore, ACLF occurs in young patients (mean age 52 years) and about 50% have no knowledge of their underlying cirrhosis. Indeed, in about 40% patients, no precipitating event can be identified. A prospective observational study of hospitalized patients with cirrhosis in 2013 by the European Association for the Study of the Liver-Chronic liver failure (EASL-CLIF) Consortium, the EASL-CLIF Acute-on-Chronic Liver Failure in Cirrhosis (CANONIC), the largest and most comprehensive registry on ACLF to date, showed a 28 day

Clinical Investigation Plan	CIP YAQ-002	Version: 7.0 10 October 2019
-----------------------------	-------------	------------------------------

mortality of 22%, 32% and 78% for ACLF grades 1, 2 and 3, respectively. [6]. The diagnosis of ACLF is made using the CLIF Consortium organ failure scores (CLIF-C OFs), the prognosis of these patients using the CLIF Consortium ACLF score (CLIF-C ACLF), and ACLF severity grades defined using the CLIF-OF organ failure score [8], In the CANONIC study two organs, the kidneys and the brain, were found to be of particular significance in determining short term mortality. More recent studies suggest that even milder degrees of renal impairment in cirrhosis, not in the 'failure' range of the CLIF-OF scoring system, may be associated with development of ACLF and significant mortality. This refers to the subgroup(1b) of stage 1 AKI defined by a serum Creatinine (sCr) at presentation of above 1.5 mg/dL [9]. As for brain dysfunction, mild hepatic encephalopathy (HE) particularly grade 1 HE may not be consistently reproducible using the West Haven criteria, and as such is now included as part of the covert HE spectrum along with minimal HE [10] often requiring psychometric tests or EEG for diagnosis.

Additioally, post-hoc analysis of CANONIC data has identified rapidly progressive hyperbilirubinaemia with a serum bilirubin level greater than 20 mg/dL at the time of presentation as a single hepatic organ failure being associated with poor prognosis. This criterion was also used in the RELIEF study, the only randomized controlled trial to date of MARS therapy in ACLF [11].

2.8 Rationale for utilising DIALIVE device for ACLF patients

The novelty of DIALIVE is that it incorporates albumin removal (and replacement) and endotoxin removal, which has not been applied before into one device. DIALIVE has powerful and selective toxin elimination (using an endotoxin-specific filter adsorber, oXiris®, and replacement of defective albumin (SepTex™ filter plus fresh albumin reinfusion) functions while preserving other important plasma proteins. The two filters used are already CE-marked and have been on the market since 2010 to treat sepsis, Acute Kidney Injury (AKI) and Continuous Renal Replacement Therapy (CRRT).

The currently available Liver Dialysis Devices (LDDs) are based on the principal of removal of protein bound and water soluble substances (blood purification) by albumin dialysis, by plasma separation and filtration or by therapeutic plasma exchange. Devices based solely on the removal of water soluble substances (blood detoxification) have not shown any benefit in survival, possibly because of the limited, non-specific absorptive capacity of chemical adsorbents. Recent clinical trials of MARS [11] and Prometheus [12], devices based on the principles of albumin dialysis, in patients with ACLF failed to demonstrate a survival benefit compared to standard medical treatment. In these clinical trials the oxidized fractions of human mercaptalbumin (HMA, non-oxidized), human nonmercaptalbumin-1 (HNA1, reversibly oxidized) and human nonmercaptalbumin-2 (HNA2, irreversibly oxidized), were markedly increased. Both MARS and Prometheus treatments resulted in a shift of HNA1 to HMA while HNA2 was not significantly affected. This shift in albumin fraction was transient and disappeared within 24 hours after treatment. There were no significant differences between MARS and Prometheus treatments with respect to the redox state of albumin.

From the pathophysiological perspective, ACLF is characterised by systemic inflammation and endotoxaemia. The severity of neutrophil dysfunction has also been shown to correlate with the risk of death of ACLF patients [13]. The mechanism of this immune failure is unclear but studies have clearly demonstrated that the defects in neutrophil function can be reversed if the patient's neutrophil is incubated with normal plasma. In addition, incubation of normal neutrophils with patient plasma makes them dysfunctional, assuming the patient phenotype [13, 14]. These observations suggest that the plasma can transmit the neutrophil functional defect. Further studies showed that this substance in plasma was an 'endotoxin- like substance' suggesting that removing this from the plasma could prevent immune failure and possibly consequent infection in ACLF patients. This rapidly evolving cycle of inflammation / hepatocyte cell death / immune failure / exacerbation of liver failure is referred to as the ACLF spiral. The data support the hypothesis that targeting inflammation may prevent cell death, and endotoxin removal may prevent immune failure thereby reducing the risk of infection and

Clinical Investigation Plan CIP YAQ-002 Version: 7.0 10 October 20	19
--	----

mortality.

DIALIVE targets the ACLF spiral with a combination of albumin removal and replacement and, endotoxin removal; thereby reducing systemic inflammation. The results of these studies led to the hypothesis that a combination of albumin removal and replacement and, endotoxin removal may be useful to treat patients with liver failure. In both cases, achieving an improvement by 20% would result in improved survival.

Importantly, all current LDDs have limited effect on inflammation and do not restore albumin function. DIALIVE addresses these deficiencies and replaces irreversibly destroyed albumin and removes endotoxin.

The success of the DIALIVE observed in animal models is related to its ability to efficiently remove endotoxin and irreversibly oxidized albumin (human non-mercapt albumin-2; HNA-A2). Thus the combination of endotoxin and damaged-albumin removal followed by fresh albumin infusion improved liver function and mostly importantly markedly increased the survival of pigs.

2.9 Findings of pre clinical work

Pre-clinical data (animal)

Two animal studies were performed (n=29 pigs); 13 in study 1 and 16 in study 2 in clinically-relevant, fully monitored pigs with paracetamol-induced acute liver failure that were managed in an intensive care unit setting with full supportive therapy to generate proof of concept data. This model was chosen because it exhibits the key pathophysiological features of ACLF [15]

- a. Multiorgan dysfunction manifested by severe encephalopathy, renal failure and consequent mortality.
- b. Biochemical evidence of liver injury, coagulopathy and lactatemia.
- c. The classical pathophysiological factors the DIALIVE device is designed to address and is found in patients with liver failure:
 - (i) albumin dysfunction
 - (ii) endotoxemia and consequent neutrophil dysfunction

Animal Study 1: [Funded by DoH, HTD-420]: Performed in Tubingen, Germany. N=13 pigs were randomised to standard of care or device treatment, using an early version of DIALIVE (using non-CE marked filters). The results showed safety and biocompatibility of the device with significant improvement in the key variables such as the severity of endotoxemia, albumin and neutrophil dysfunction. Difference in survival between the two groups using a log-rank test was, p=0.02. The hazard ratio (Control:Device) was 5.45 (95% CI 1.1-26.4). This device however, will not be CE marked and it was thought that the results were too variable for translation into man. Therefore, additional studies were performed using an improved device design, which can be directly translated into man (Animal Study 2, see below).

Animal Study 2: [Funded by MRC-DPFS G09221]: Was performed using the current version of the device to be CE marked. In the first part, the data showed that an improved biological and clinical effect with the use of both filters together, producing a synergistic benefit. In the second part, n=16 pigs were studied in a randomised, blinded clinical trial to receive standard of care or treatment with DIALIVE [5].

Briefly, the results showed:

- a. Safety, biocompatibility and ease of use with a set up time of less than 2 hours.
- b. Difference in survival between the two groups using a log-rank test was, p=0.02. The hazard ratio (Control:Device) was 3.81 (95% CI 1.2-12.4).
- c. Improved clinical condition: The animals required significantly less fluid support and had better respiratory function in the DIALIVE group.
- d. The severity of endotoxemia, neutrophil and albumin dysfunction was attenuated in the DIALIVE animals.

Clinical Investigation Plan	CIP YAQ-002	Version: 7.0 10 October 2019
-----------------------------	-------------	------------------------------

The optimized DIALIVE used in animal study 2 was easy to use with a set-up time of 1.6-2 hours. No device failures were observed, and circuit clotting requiring change of filter was also not observed. Device related complications such as embolism, bleeding or DIC were not observed in any of the animals studied. The vascular catheters used were the same as that used in humans for haemofiltration, and no device related issues were observed.

The results of the above animal studies demonstrated that DIALIVE was safe and increased survival of the pigs treated with the device compared with untreated controls.

Pre-clinical data (in-vitro study)

A further laboratory based study was devised to investigate and quantify the removal of a range of biological markers, including endotoxin, from whole blood *in vitro* and when using the DIALIVE system as configured in the clinical trial, i.e. oXirs plus septeX plus connecting tubing mounted onto the Prismaflex. This preliminary data will be used to support the continuing European multi-center, first into man, clinical investigation, which is currently underway. The methods, results and conclusions are listed in the IB v 3.0. The main results and conclusions from the *in vitro* tests are:

- The system demonstrated effective clearance of small molecules as expected;
- The progressive removal over time of albumin across the filters was demonstrated: total albumin removal amounted to 6.5g/L, or the equivalent of 1.1g/L/hr.
- Consistent removal of endotoxin was demonstrated using the chromogenic LAL assay.

We feel the results seen from the previous animal studies and the results obtained from the recent *in vitro* study, continues to support the hypothesis for the ongoing first into man clinical investigation which is currently underway.

